Due to the availability of other more conveniently administered therapies e.g. oral, once daily (QD), or once weekly (QW), recruitment to this study has been slow/difficult despite extensive efforts by the sponsor. The planned number of patients will take unreasonably long to recruit so a decision was made with agreement by the European Medicines Agency and Food and Drug Administration to stop recruitment and to pool patients from both exenatide arms and compare the pooled arm with placebo. With a total of 122 patients randomized (Total EBID:Placebo 2:1), the study should have approximately 87% power to detect a difference between Total EBID and placebo assuming the true mean changes in HbA1c are -0.7, -0.5, and 0 for patients receiving exenatide 10 µg BID, exenatide 5 µg BID, and placebo BID, respectively. The combined effect of the Total EBID doses compared to placebo (mean difference) is assumed to be -0.6 with a common standard deviation of 1% at the 5% significance level without consideration of patient discontinuation and impact on effect size. An assumed effect size of -0.455 was considered in power calculation.

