3.5 Exploratory safety variables

The exploratory safety endpoint is change in estimated glomerular filtration rate (eGFR) from baseline Visit 3 (Week 0) to Visit 11 (Week 28).

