4.1.2 Hypothesis testing significance level

Statistical tests, where performed, will be conducted at a 2-sided significance level of 5%. Where appropriate, model-based point estimates, together with their 95% confidence intervals will be presented along with the 2-sided p-values for the tests.

No adjustments for multiplicity (including hierarchical testing) will be made for the primary, secondary and exploratory variables.

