Secondary 2	Evaluable	Change in HbA1c from baseline to Week 28 and each intermediate visit	All IEs: Data after event excluded. Hypothetical approach due to missing at random (MAR) assumption of MMRM analysis	Least squares mean difference in CFBL at Week 28 and each intermediate visit between Total EBID and PBO

	Attributes			
Estimand	Population	Variable	Intercurrent event (IE) strategy	Population-level summary
Sensitivity to secondary 2	Evaluable	Change in HbA1c from baseline to Week 28 and each intermediate visit	All IEs: Data after event excluded. Hypothetical approach using multiple imputation (MI) pattern mixture modelling	Least squares mean difference in CFBL at Week 28 and each intermediate visit between Total EBID and PBO
Continuous secondary and exploratory efficacy endpoints measured post-baseline at a single endpoint	Full analysis set	Change in XX* from baseline to Week 28	All IEs: Data after event excluded. Hypothetical approach due to missing at random (MAR) using MI ANCOVA analysis	Least squares mean difference in CFBL at Week 28 between Total EBID and PBO
Other continuous secondary and exploratory efficacy endpoints	Full analysis set	Change in HbA1c from baseline to Week 28 and each intermediate visit	All IEs: Data after event excluded. Hypothetical approach due to missing at random (MAR) assumption of MMRM analysis.	Least squares mean difference in CFBL at Week 28 and each intermediate visit between Total EBID and PBO
Exploratory	Safety	Change in eGFR from baseline to Week 28 by baseline eGFR category	All IEs: Data after event excluded. Hypothetical approach due to MAR assumption of MMRM analysis.	Least squares mean difference in CFBL at Week 28 between Total EBID and PBO
Sensitivity to exploratory	Safety	Change in eGFR from baseline to Week 28 by baseline eGFR category	Rescue and IP discontinuation: Data after event included. Treatment policy approach.	Least squares mean difference in CFBL at Week 28 between Total EBID and PBO

	Attributes			
Estimand	Population	Variable	Intercurrent event (IE) strategy	Population-level summary
			Withdrawal from study prior to Week 28: Hypothetical approach due to MAR assumption of MMRM analysis.	

*where XX are FSG, FSI, SMBG, HOMA-B, HOMA-S, hip and waist circumference.

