4.2.5.4 Laboratory data (including CEA and calcitonin concentrations)

Continuous laboratory parameters will be summarized in standardized international (SI) and US units. The visit windows described in Section 4.3.2 will be used. There will be no imputation for missing values.

All hematology, clinical chemistry and urinalysis results will be listed by treatment group, patient, and visit, including scheduled and unscheduled/repeat measurements. Laboratory assessments that are outside of normal ranges will be flagged. Separate listings of laboratory values above/below the upper/lower limit of the reference range will be produced. The central laboratory or local laboratory (for assessments measured at a local laboratory) reference ranges will be used. The observed values at each visit to Visit 11 (Week 28) and change from baseline values will be summarized for each of the quantitative laboratory assessments by treatment group for the Safety analysis set. For categorical parameters, shift tables from baseline to each visit to Visit 11 (Week 28) will be produced by treatment group for the Safety analysis set. Tumor marker CEA and calcitonin levels will also be summarized by visit for the Safety follow-

up analysis set. These summaries will include observed values at each visit from Visit 3 (Week 0) through Visit 11 (Week 28) to end of the safety follow-up period and change from baseline by actual treatment group during the randomized period and overall.

Number and percentage of laboratory results that are potentially clinically significant (see Appendix 6) will be listed and summarized by analyte name and criteria for each treatment group for the safety analysis set. A listing of calcitonin values >100 ng/L will be produced.

Estimated glomerular filtration rate (eGFR) will be derived based using the Bedside Schwartz formula (Schwartz, 2009):

$$\text{eGFR} = 41.3 * (\text{Height in meters} / \text{Serum creatinine in mg/dL})$$

A table of observed and change from baseline in eGFR values will be provided. This will be provided both overall and by baseline eGFR, hyperfiltrating versus non-hyperfiltrating, where hyperfiltration is defined as an eGFR ≥ 125 ml/min/1.73m².

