An ANCOVA analysis of change in eGFR from baseline to Week 28 by baseline eGFR (hyperfiltrating: ≥ 125 ml/min/1.73m² versus non-hyperfiltrating: < 125 ml/min/1.73m²) will be provided. The same multiple imputation approach as stated in Section 4.2.4.4 will be used. The model will include treatment, screening HbA1c strata ($\leq 8\%$, $> 8\%$), background diabetes therapy strata (drug naïve, metformin only, SU only, and metformin + SU), baseline eGFR as the fixed effects. The least squares mean, 2-sided 95% confidence interval, and p-value of the difference in the endpoints of interests between Total EBID and PBO groups will be presented. This analysis will be done both excluding data after initiation of rescue therapy and separately including data after initiation of rescue therapy.

eGFR will also be calculated using the Chronic Kidney Disease Epidemiology Collaboration (CKD-EPI) formula (Levey et al, 2009):

$$\text{eGFR} = 141 \times \min(\text{Scr}/\kappa, 1)^\alpha \times \max(\text{Scr}/\kappa, 1)^{-1.209} \times 0.993^{\text{Age}} \times [1.018 \text{ if female, } \times 1.159 \text{ if black}]$$

where Scr is serum creatinine, κ is 0.7 for females and 0.9 for males, α is -0.329 for females and -0.411 for males, min indicates the minimum of Scr/ κ or 1, and max indicates the maximum of Scr/ κ or 1.

eGFR using the CKD-EPI equation will be summarized at baseline and may be analyzed as a sensitivity analysis.

Strip Sign for Selected Laboratory Data

For selected laboratory test values that have been received with a qualifier as a part of the result ($>$, \geq , $<$, or \leq), a process to strip the qualifier will be applied and the resulting numeric values will be used for data analysis. The raw value with operator will remain as such in the database and will be used when listed.

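### The eGFR inference is specified only by baseline category (at or above 125 versus below), with no overall treatment difference and no interaction for an endpoint listed without a split

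*SAP*

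**What the plan says.** SAP 3.5 names a single exploratory safety endpoint: "change in estimated glomerular filtration rate (eGFR) from baseline Visit 3 (Week 0) to Visit 11 (Week 28"). No subgroup is mentioned.

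SAP 4.2.5.4 then plans two things for eGFR by the Bedside Schwartz formula.

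- A descriptive table of observed values and changes: "This will be provided both overall and by baseline eGFR, hyperfiltrating versus non-hyperfiltrating".
- An inferential analysis: "An ANCOVA analysis of change in eGFR from baseline to Week 28 by baseline eGFR", with the cut at 125 mL/min/1.73 m². The model terms are treatment, screening HbA1c strata, background therapy strata and baseline eGFR. The output is a least squares mean difference between Total EBID (the pooled exenatide arms) and placebo, with 95% CI and p-value. It is run once without and once with post-rescue data, using multiple imputation.

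In SAP 4.2.4.1, Table 3, the exploratory estimand and its sensitivity version both define the variable as "Change in eGFR from baseline to Week 28 by baseline eGFR category", in the Safety set.

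A CKD-EPI version of eGFR is summarized at baseline and may be analysed as a sensitivity analysis. Whether that would be split is not stated.

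On multiplicity, SAP 4.1.2 says: "No adjustments for multiplicity (including hierarchical testing) will be made for the primary, secondary and exploratory variables".

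**The concern.** The endpoint and its inferential analysis do not match. The endpoint belongs to the whole trial, while the analysis is described only within two baseline categories. The descriptive table is given overall and by category, and the ANCOVA sentence that follows drops the overall part.

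Two things follow on the plain reading. First, the most precise summary of the treatment effect on eGFR, the whole-trial difference with its interval, is not specified. That matters because Protocol 4.1 mentions postmarketing renal reports, and SAP 6 adds eGFR beyond the protocol because it may be informative. Second, readers would see one p-value for each category and nothing that compares the categories. One significant and one non-significant result would invite a claim that the drug acts on eGFR only in hyperfiltrating patients, or only in the others.

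**Working it through.** **Inputs from the documents.** 122 patients randomized, Total EBID to placebo 2:1 (SAP 1.3); two-sided 5% tests without adjustment (SAP 4.1.2).

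**Inputs not in the documents.** The eGFR effect, its SD, a power target and the share of patients at or above 125. The share s is varied below. Equal SD, a 2:1 ratio and the same treatment effect in each category are assumed. Baseline eGFR is not a randomization stratum, so 2:1 within a category holds only on average.

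**Check of sample size and allocation.** The only power figure for the pooled comparison is for HbA1c: difference 0.6, SD 1.0, about 87%. The standard error is √(1/40.67 + 1/81.33) = 0.192, and 0.6/0.192 = 3.124. Power is Φ(3.124 − 1.96) = 87.8%. The noncentral t version gives 87.4% with 81:41 and 87.0% with 82:40. The stated figure reproduces, so 122 at 2:1 is the right base. It says nothing about power for eGFR.

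**Precision.** With N patients at 2:1, the standard error in SD units is √(1/(N/3) + 1/(2N/3)) = √(4.5/N). In a category holding share s it is √(4.5/(sN)), so the interval widens by 1/√s. This ratio needs no assumed effect and does not depend on N.

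| Patients | SE (SD units) | 95% half-width (1.96 × SE) | Ratio to overall |
|---|---|---|---|
| All, N = 122 | 0.192 | 0.38 | 1.00 |
| Share 50% (61) | 0.272 | 0.53 | 1.41 |
| Share 80% (97.6) | 0.215 | 0.42 | 1.12 |
| Share 20% (24.4) | 0.429 | 0.84 | 2.24 |

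A 20% category would hold about 16 exenatide and 8 placebo patients. A separate model there would fit 7 parameters: intercept 1, treatment 1, screening HbA1c 1, background therapy 3, baseline eGFR 1.

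**Power, as illustration.** If the overall comparison had power P0, category power is Φ((1.96 + z(P0))·√s − 1.96). For P0 = 80%, 1.96 + 0.84 = 2.80.

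- 50:50: Φ(2.80 × 0.707 − 1.96) = 50.8% in each.
- 40:60: 42.5% and 58.3%.
- 20:80: Φ(2.80 × 0.447 − 1.96) = 24.0%, and Φ(2.80 × 0.894 − 1.96) = 70.7%.
- 10:90: 14.1% and 75.7%.

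**How often a uniform effect looks differential.** Under the same assumptions, with the same true effect in both categories, the chance that exactly one category is significant is p1(1 − p2) + p2(1 − p1).

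- 50:50: 2 × 0.508 × 0.492 = 50%.
- 20:80: 0.240 × 0.293 + 0.707 × 0.760 = 61%.

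With no effect in either category, at least one false positive has probability 1 − 0.95² = 9.75%.

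**The SAP's own practice.** For HbA1c, SAP 4.2.4.2 estimates the overall difference first and then adds treatment-by-baseline and treatment-by-strata interactions to examine homogeneity. Nothing comparable is listed for eGFR.

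**The case against.** Several points on the other side are fair.

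- **The text is ambiguous.** SAP 4.2.5.4 speaks of one model and one difference, and Table 3 gives a single difference in the Safety set. This could mean one overall estimate. But the reference to baseline category would then have no defined role, so the wording needs correcting on either reading.
- **A reader might infer that eGFR is never compared across the whole trial.** The documents do not support that. The descriptive table is planned overall, and the optional CKD-EPI analysis has no stated split. What is missing is a specified overall inferential comparison.
- **A reader might infer a fixed power loss of about 30 points.** The figure 80% − 50.8% = 29.2 points needs an assumed 80% overall power and an even split, neither of which is in the documents. With 80% overall and category shares from 10% to 90%, the loss runs from about 66 down to 4 points.
- **A reader might infer that a renal effect would be missed altogether.** The chance that at least one category is significant is 1 − (1 − 0.508)² = 75.8% at an even split, close to 80%. The cost lies more in width and interpretation, and in two unadjusted tests.
- **The form of baseline eGFR in the model is not stated.** Table 2 lists it both as continuous and in categories, so it cannot be assumed to be continuous.
- **Category estimates are a legitimate exploratory aim.** An average could hide opposing changes. That supports keeping them; it is no reason to omit the overall estimate or the interaction.

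The endpoint is exploratory with no power target, which limits the weight of the point.

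**Conclusion.** The point holds in a limited form. On the plain reading, an endpoint listed for the whole trial has no specified overall treatment difference with a confidence interval, and nothing tests whether the effect differs by baseline eGFR.

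The firmest measure of cost is the 1/√s widening, which rests only on equal SD and the same allocation ratio in each category. The power and misreading figures also assume 80% overall power and a common effect, and they illustrate the problem without being properties of this plan. No size can be fixed until the share at or above 125 is known. This does not touch the primary analysis. It is a low-cost improvement in precision and clarity.

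**What to change.** In SAP 4.2.5.4 and Table 3:

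1. Make the main eGFR analysis one ANCOVA on all Safety-set patients, on the same imputed datasets, with treatment, continuous baseline eGFR, screening HbA1c strata and background therapy strata. Report the Total EBID minus placebo difference with 95% CI.
2. Add treatment-by-baseline-eGFR to that model, as is done for HbA1c, and report the interaction with its CI. It will be imprecise. In two-category form its standard error is 1/√(s(1 − s)) times the overall one: 2.0 at 50:50 and 2.5 at 20:80. A non-significant interaction should therefore not be taken as evidence of a common effect.
3. Keep the estimates for at or above 125 and below 125, with CIs, as supportive subgroup results.
4. Reconcile the method. Table 3 names MMRM for eGFR, while 4.2.5.4 names multiple-imputation ANCOVA. Chemistry is scheduled after baseline only at Visit 11 or early discontinuation, and SAP 4.1.5 assigns ANCOVA to endpoints measured once. Also correct the pointer in SAP 6, which sends the reader to 4.2.4.5 for the eGFR analysis.

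The cost is a few lines of SAP text and two further model fits on data already imputed. The downside is one more exploratory table and less prominence for the category p-values.

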4.1.3.3 Missing safety data

Safety analyses will be conducted on the observed case (OC) only.

However, imputation of missing or partial AE and concomitant medication onset/start, and end/stop dates will be used to determine the status of each AE and the previous/concomitant status of each medication. See [Appendices 3 and 4](#) for the method of imputation of missing/partial AE/concomitant onset/start and end/stop dates. Missing/partial start/stop dates will appear as is (i.e., without imputation) in the patient data listings, but will be imputed to permit the proper tabulation of AE and concomitant medications data.

In addition, in case of missing AE severity, AE causality, or AE seriousness, a worst-case approach will be used. For missing severity, the AE will be considered severe; for missing causality, the AE will be considered as possibly-related to study drug; for missing seriousness, the AE will be considered serious.

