4.1.4 Handling of data post rescue medication

Instances of patients receiving rescue medication is defined in Section 3.6.4.

Efficacy

For all efficacy endpoints data collected after the first administration of rescue therapy will be excluded from the descriptive statistical summary and inferential statistical analyses.

However, data collected after initiation of rescue medication will be included in several sensitivity and supportive analyses for the primary analysis to provide a comprehensive view of the treatment effect (see more details in Section 4.2.4.3).

Safety

Because patients can continuously receive study medication concurrent with the rescue therapy, all safety data (except eGFR) collected during the rescue medication use will be summarized together with data collected prior to the rescue therapy. The exploratory analysis of eGFR will be repeated twice (once including data after rescue therapy and once excluding data after rescue therapy).

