4.1.5 Statistical modelling

In general, continuous variables will be analyzed using a MMRM if multiple post-baseline measurements are collected. If only an endpoint measurement is collected, analysis of covariance (ANCOVA) will be used. The MMRM/ANCOVA analysis will be treated as the primary analysis method for continuous efficacy endpoints. The statistical analysis of categorical variables will be done using a stratified Cochran-Mantel-Haenszel (CMH) test.

Standard diagnostic approaches will be used to verify that the key statistical assumptions of the MMRM/ANCOVA and CMH test hold.

If the distributional assumptions of the MMRM for the primary analysis do not hold, alternative models will be explored using appropriate transformed data.

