4.2.4 Efficacy analysis

4.2.4.1 Estimands

Estimands for the study are defined in Table 3. Intercurrent events (IE) that may occur during the study are receipt of rescue therapy, IP discontinuation and study withdrawal.

Table 3 Estimand framework

Estimand	Attributes			
	Population	Variable	Intercurrent event (IE) strategy	Population-level summary
Primary	Evaluable	Change in HbA1c from baseline to Week 28	All IEs: Data after event excluded. Hypothetical approach due to missing at random (MAR) assumption of MMRM analysis.	Least squares mean difference in CFBL at Week 28 between Total EBID and PBO
Sensitivity to primary	Evaluable	Change in HbA1c from baseline to Week 28	All IEs: Data after event excluded. Hypothetical approach using multiple imputation (MI) pattern mixture modelling.	Least squares mean difference in CFBL at Week 28 between Total EBID and PBO
Supplementary to primary	Evaluable	Change in HbA1c from baseline to Week 28	Rescue and IP discontinuation: Data after event included. Treatment policy approach Withdrawal from study prior to Week 28: Hypothetical approach due to MAR assumption of MMRM analysis	Least squares mean difference in CFBL at Week 28 between Total EBID and PBO

	Attributes			
Estimand	Population	Variable	Intercurrent event (IE) strategy	Population-level summary
Sensitivity to supplementary of primary	Evaluable	Change in HbA1c from baseline to Week 28	Rescue and IP discontinuation: Data after event included. Treatment policy approach Withdrawal from study prior to Week 28: Hypothetical approach using MI pattern mixture modelling	Least squares mean difference in CFBL at Week 28 between Total EBID and PBO
Secondary 1	Evaluable	Proportions of patients having HbA1c goals of <7%, ≤6.5%, and <6.5% at Week 28	All IEs: Data after event excluded. Composite approach used, with patients with missing data at endpoint treated as non-responders	Difference in proportion of responders at Week 28 between Total EBID and PBO
Sensitivity to secondary 1	Evaluable	Proportions of patients having HbA1c goals of <7%, ≤6.5%, and <6.5% at Week 28	All IEs: Data after event excluded. Hypothetical approach using MI pattern mixture modelling	Difference in proportion of responders at Week 28 between Total EBID and PBO

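### The two planned eGFR runs in SAP 4.1.4 and 4.2.5.4 split only on rescue, whereas the estimand table also splits on stopping study drug, so off-drug creatinine stays in a run from which Table 3 excludes it

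*SAP*

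**What the plan says.** SAP 4.2.4.1 names the intercurrent events for the whole estimand table: "Intercurrent events (IE) that may occur during the study are receipt of rescue therapy, IP discontinuation and study withdrawal". Table 3 then has two rows for the variable "Change in eGFR from baseline to Week 28 by baseline eGFR category", both in the Safety set.

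- The Exploratory row (called the main row here) reads: "All IEs: Data after event excluded. Hypothetical approach due to MAR assumption of MMRM analysis".
- The row for sensitivity to exploratory reads: "Rescue and IP discontinuation: Data after event included. Treatment policy approach". Study withdrawal is left to the missing-at-random assumption.

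SAP 4.2.5.4 specifies the analysis itself: an ANCOVA with multiple imputation, comparing Total EBID with placebo. On which data enter, it says only: "This analysis will be done both excluding data after initiation of rescue therapy and separately including data after initiation of rescue therapy". SAP 4.1.4 gives the same pair of runs, again divided on rescue alone.

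Three further passages bear on the method. SAP 4.1.5 says: "If only an endpoint measurement is collected, analysis of covariance (ANCOVA) will be used". SAP 4.1.3.3 says: "Safety analyses will be conducted on the observed case (OC) only". The opening paragraph of SAP 4.2.5.4 rules out imputing missing laboratory values.

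**The concern.** Table 3 and the analysis sections disagree about creatinine drawn after a patient has stopped study drug but before the treatment period closes. Table 3 keeps such values out of the main estimate and brings them back in the sensitivity estimate. The analysis sections say nothing about them, and the visit conventions then let them in.

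This decides whether the main eGFR estimate describes patients on drug or mixes on-drug and off-drug values. Any renal effect that reverses on stopping would be diluted in the mixture. eGFR appears to be the only safety variable for which the SAP plans a modelled treatment difference with a confidence interval and p-value. Protocol 4.1 notes postmarketing reports of altered renal function, and SAP Section 6 adds eGFR because it may be informative. If the conflict is still open at unblinding, the choice between passages becomes post hoc.

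**Working it through.** The documents give no eGFR effect, standard deviation or power, so there is no stated figure to reproduce. The check sets the passages side by side and then bounds the size.

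**Step 1. Which data enter each analysis**

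| Specification | After rescue | After IP discontinuation |
|---|---|---|
| Table 3, main row | out | out |
| Table 3, sensitivity row | in | in |
| 4.1.4 and 4.2.5.4, first run | out | no rule |
| 4.1.4 and 4.2.5.4, second run | in | no rule |

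**Step 2. What happens where there is no rule**

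- Chemistry is drawn after baseline only at Visit 11 or ED (Protocol Attachment 1; SAP Appendix 1).
- SAP 3.6.6 ends the treatment period at the ED visit for patients who leave before Week 28.
- SAP Table 9 gives laboratory values a single post-baseline window in that period, from Day 2 to its last day, labelled Week 28.
- An ED creatinine therefore becomes the Week 28 value in both runs. The exception is a patient who had also started rescue before the sample, whose value the first run drops.

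**Step 3. Whether off-drug ED samples are foreseeable**

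Protocol 7.4 and 8.8 discontinue patients who miss more than 10 consecutive days of study drug. For them the ED sample would normally come after a drug-free gap. SAP 4.2.5.1 allows for an ED visit later than the last dose. SAP 3.6.5 asks for the visit as soon as possible, so for other patients the gap may be short or nil.

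**Step 4. Size**

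Let d be the fraction of exenatide patients whose Week 28 value is an off-drug ED value, and r the fraction of the effect lost by then. The estimate becomes (1 − d × r) times the on-drug effect.

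- d = 0.23 (SAP 1.3, exenatide arms, from an earlier study) and r = 1: 1 − 0.23 = 0.77, a shrinkage of 23%.
- d = 0.10, r = 1: 0.90. d = 0.35, r = 1: 0.65. These two rates are assumptions to show the range.
- r = 0, or every ED sample on the discontinuation date: 1.00, no shrinkage.

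At 23%, with 122 randomized 2:1, the exenatide patients concerned number at most 0.23 × 122 × 2/3 = 18.7, about 19. Placebo patients have no drug effect to lose.

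**Step 5. Data rule against method label**

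A simulation used 300 trials of 122 patients, 2:1, with one post-baseline value, 23% off drug in each arm, an effect of 1 SD on drug and none off drug. Mean estimates were:

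- ANCOVA on observed on-drug values: 0.99
- the same with missing-at-random multiple imputation: 0.99 (mean absolute difference from the first, 0.006)
- ANCOVA with off-drug values included: 0.76

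The data rule moves the estimate. The choice between observed cases and imputation hardly does. With a single post-baseline value, an MMRM reduces to an ANCOVA.

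**The case against.** **Table 3 is the only passage with an IP-discontinuation rule for eGFR, and silence elsewhere does not revoke it.** This is fair, and it limits the claim. No passage states that off-drug creatinine is included; inclusion follows from silence plus the visit window. But 4.2.5.4 is the section a programmer would follow, and its two runs, as worded, do not yield the two Table 3 estimands.

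**The exclusions in SAP 4.2.4.2 and 4.2.4.4 may carry over.** The first mentions ANCOVA as well as MMRM, and 4.2.5.4 borrows its imputation approach from the second. This is arguable but not settled. Both passages sit under primary and secondary efficacy variables, and SAP 3.5 classes eGFR as exploratory safety.

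**A reader might infer that the three method statements (MMRM, imputed ANCOVA, observed cases) themselves put off-drug values both in and out.** The documents do not support that. Method and imputation do not decide which values enter. SAP 4.1.5 already points to ANCOVA for a single endpoint measurement, and the specific eGFR text reasonably overrides the general observed-case rule. The no-imputation sentence follows directly on one about summarizing laboratory parameters, so it can be read as covering summaries only. These are labels to tidy.

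**A reader might also infer that some 28 patients (0.23 × 122) have a disputed value.** That would need the exenatide planning rate to hold in placebo too, and every discontinuer to attend ED and be sampled after the discontinuation date. The documents give none of this.

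**Conclusion.** The conflict over data after IP discontinuation is real. If 4.1.4 and 4.2.5.4 are followed as written, an ED creatinine taken off drug, without prior rescue, counts as a Week 28 value in both runs, and the contrast defined in Table 3 is not produced.

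The effect on the estimate runs from no change to a shrinkage of about 23%. The upper end assumes that the 23% planning rate holds, that every exenatide discontinuer gives an off-drug ED sample without earlier rescue, and that the effect has fully reversed by then. The documents establish none of these, nor that the drug affects eGFR at all, so the figure is a bound at that rate and not a forecast.

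Severity is minor. eGFR is exploratory, it is not a protocol endpoint, and the primary HbA1c conclusion does not depend on it.

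**What to change.** In SAP 4.1.4 and 4.2.5.4, state that the main eGFR analysis excludes data after rescue or after the date of IP discontinuation, and that the sensitivity analysis includes both, as in Table 3. Say which run is the main one.

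As tidying with little numerical effect:

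- in the two eGFR rows of Table 3, replace MMRM with multiple-imputation ANCOVA;
- exempt the eGFR model from the observed-case sentence in 4.1.3.3 and the no-imputation sentence in 4.2.5.4;
- correct SAP Section 6, which sends the reader to 4.2.4.5 for an eGFR analysis that is not there.

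The cost is SAP wording plus one filter on the IP discontinuation date in the main run. No new data are needed. The change should be made before unblinding.
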